Risks Associated with Intradermal Microdialysis: Research techniques are only performed by personnel who are trained and approved by [name] to complete these procedures. [name] has 10 years of experience utilizing intradermal microdialysis without unanticipated adverse events. All laboratory personnel are trained in CPR and basic first aid. In the event of a life threatening emergency, lab personnel call 911. The PSRB is equipped with AED and lab personnel are trained in how to use them if necessary. Prior to placing the microdialysis fibers, the researcher puts on sterile gloves and cleans the skin with iodine and alcohol to reduce the risk of infection. The researchers apply ice to the skin for 5 minutes before placing the microdialysis fibers to reduce any pain associated with placement. Once the fibers are in place, research personnel constantly monitor subjects for adverse reactions (e.g. pain, itching, redness, swelling) to the microdialysis fibers or the perfusates. Participants are never left unsupervised with the fibers in place. An automated monitor measures blood pressure every 5 minutes and constantly records heart rate. The researchers clip the ends of the fibers and clean them with an alcohol swab before removing them from the skin to reduce the risk of infection. They stop any bleeding by applying mild pressure to the sites with a sterile gauze pad. The researchers apply a clean, sterile bandage to the area before the participant leaves. Participants are given verbal and written instructions on how to care for the sites and to call [name] or the research nurse if they have any questions or concerns about the sites after they have left the study visit.

Risks associate with blood draw: Only appropriate trained laboratory personnel perform the blood draw procedure. A sterile gauze pad and pressure wrap (latex free coban) are applied to the site after the blood draw to stop any bleeding and minimize bruising.

Risk of loss of confidentiality: The investigators collect the minimum amount of confidential data in order to complete the aims. All subjects are assigned a code and data and specimens are collected using the code only. The only time subject names and codes appear together is on their file which is kept in a locked cabinet in the PI's office. Only IRB approved personnel have access to these files. All data files are stored on password protected computers and servers and only IRB approved personnel have access. Extensive details on how the risk of loss of confidentiality is minimized are provided in section X. Privacy and Confidentiality.

Laboratory Space: The Microvascular Physiology Lab (118 PSRB) is a designated laboratory space on the University of Iowa campus. It is fully compliant with Environmental Health and Safety standards and undergoes annual inspection. The lab space is equipped with state of the art equipment to perform the proposed research procedures. All equipment is certified for human use and checked and calibrated before each experiment. The lab is equipped with a first aid kit and all lab personnel are trained in CPR and basic life support. An AED is located in the hallway just outside the lab space.

VIII.3

Does this study have a plan to have an individual or committee review combined data from all subjects on a periodic basis (such as summary or aggregate safety and/or efficacy data)?

No

IX. Benefits

IX.1

What are the direct benefits to the subject (do not include compensation or hypothesized results)?

The study procedures and/or findings do not provide direct benefits to the subjects participating in the study. Subjects receive a medical screening that could inform them about their health, including resting heart rate and blood pressure measurements. We can provide subjects with their heart rate and blood pressure values if they ask, but we will not advise them on any unexpected findings.

IX.2

What are the potential benefits to society in terms of knowledge to be gained as a result of this project?

Pre-menopausal women have significantly lower incidence of cardiovascular disease (CVD) than age-matched men due to the protective benefits of estrogen. Estrogen decreases levels of Angiotensin II, allowing less Angiotensin II to act on its receptors: AT1Rs (cause constriction) and AT2Rs (cause dilation). Excess Angiotensin II disrupts the balance between these two receptors in the body acts mainly through AT1Rs, leading to higher risk of CVD and related diseases. Because estrogen downregulates Angiotensin II, there is a balance between activation of AT1Rs and AT2Rs. In young males, this balance can be dysregulated when excess Angiotensin II is produced. A new pharmacological agent, known as Compound 21, activates AT2Rs to cause vasodilation. Besides vasodilation, activation of AT2Rs with Compound 21 also elicits anti-inflammatory and anti-fibrotic effects in animal models. In humans, this compound has been shown to cause dilation in the lungs and the peripheral vessels (e.g., skin) when given orally. Thus, the purpose of this study is to determine the extent that dilation with AT2R activation differs in young men and women. As young women have more protection from heart diseases than age-matched young males, we propose that activation of AT2Rs will be more sensitive in young women than in young men. This will help us better understand why women have enhanced cardioprotection prior to menopause.

X. Privacy & Confidentiality

X.1

What are you doing to protect the privacy interests of the subjects?

The minimum amount of data necessary to complete the aims will be collected during the study. Data are collected about the subject's normal daily activities (physical activity, nutrition, etc.) as these factors all can influence a person's vascular function. Differences in our data may be explained by these variables, which we can then confirm by looking back at their health history questionnaire when discrepancies arise. The informed consent process will be conducted in a private exam room in the private lab (118 PSRB) with the door closed. All screening and experimental procedures will be conducted in the laboratory in 118 PSRB with the door closed and locked. Only personnel directly involved in the study will be allowed in the rooms.

X.2

Are you collecting the Social Security Number of any subjects for any purpose?

No

X.4

How will information/data be collected and stored for this study (check all that apply):

- Electronic records (computer files, electronic databases, etc.) - Data will be entered using subject ID code into the ICTS REDCap web-based database application that is password protected. REDCap questionnaires will be filled out on the participants electronic device (e.g. phone, tablet, personal computer) or a printed paper copy if they prefer. No personal identifiable data will be entered. Only research staff on the IRB approved study will be allowed access this database. The ICTS REDCap staff are responsible for maintaining security of the data. Some data using subject ID code will also be entered into a Microsoft Excel and SPSS datasheets that will be kept in a shared server for CLAS that is password protected. Only research staff on the IRB approved study will have access to the folder the study on the server.
 - Name - [REDACTED]
 - Title - IT Support Consultant
 - University Job Classification - Faculty/Staff
- Biological samples (blood draws, cheek swabs, saliva samples, tissue samples, etc.) - Blood samples will be sent to the UIHC pathology lab for analyses. Remaining biological specimens, such as blood, will be labeled with subject code, date collected and IRB protocol number and transported to the PIs laboratory (118 PSRB) in a secure unbreakable biohazard container. Samples will be stored in the PIs laboratory in a -80C freezer in 111 PSRB. All samples will be labeled with date collected and subject ID code only. No personal identifiable information will be labeled on the sample. Only the PI and her research staff will have access to the samples.
 - Name - [name]
 - Title - Assistant Professor
 - University Job Classification - Faculty/Staff
- Paper/hard copy records (hard copy surveys, questionnaires, case report forms, pictures, etc.) - Most of the data are coded and do not contain personal identifying information. Some data will temporarily contain the subject's name, address, and/or telephone number (Phone Interview Form). Documents allowing identification of participants do not leave our labs and are only available to authorized persons. Only authorized personnel may access the lab computer. Data forms containing identifiable information are shredded when no longer needed (within 5 years after publication of results). We keep data in the laboratory in locked cabinets, the password-protected folder on the secured University of Iowa RDSS server, and on password-protected computers maintained in locked laboratory rooms. Only authorized personnel have access. Coded data shared with unauthorized persons cannot be traced to individuals. The list linking code numbers to participants is not shared with unauthorized persons and destroyed when the project is completed and within 5 years of publication of the data. Screening data from subjects who are not accepted into the study are shredded when the project ends. Subjects may give permission to have their contact information retained in the investigator's secured files if they wish to be considered for participation in future studies. After we complete the study, we remove all identifiers from the data and store the data indefinitely. Individual data may be used without identifying the subject to illustrate representative responses. Any hard paper copy of subject lists or data will be kept in a locked cabinet in the locked office of the PI. Subjects will be assigned a code for the study. Files will be labeled with this code for confidentiality. Study data including laser-Doppler flowmetry data will be stored on password protected computer hard-drives and password protected server folders which are only accessible to research team members via password. Subject confidentiality will be maintained in all presentations and publications and information/records pertaining to subject participation in the research project will not be released without prior authorization by the subjects.

X.5

Do the confidentiality protections indicated above allow only members of the research team to access the data/specimens?

Yes

X.7

Does your study meet the NIH criteria for a Certificate of Confidentiality or will you be applying for Certificate of Confidentiality?

No

XI. Data Analysis

XI.1

Describe the analysis methods you will use, including, if applicable, the variables you will analyze

The primary outcome variable will be cutaneous vascular conductance, which is calculated from laser-Doppler flux/mean arterial pressure. Three-way repeated measures ANOVA (group, MD site, dose) will be used to examine group differences and local microdialysis treatment differences across the doses of pharmacological stimuli. Appropriate post-hoc analyses with corrections for multiple comparisons will be performed when main effects are identified, including potential confounding variables as covariates. Paired t-tests will be used to examine group differences in subject characteristics.

XI.2

Provide the rationale or power analysis to support the number of subjects proposed to complete this study.

Using previously published data that determined differences in cutaneous vascular conductance (CVC), an index of skin blood vessel dilation, the results of a power analysis indicated that 24 young men and women (12 subjects x 2 groups) will be sufficient to detect a meaningful physiological difference (power=0.80, $\alpha=0.05$) of a ~10% change in CVC from baseline between microdialysis treatment sites and sex differences (men and women). Based on the available literature and on prior experience with microdialysis studies, the standard deviation of the difference is ~10%. After accounting for attrition, withdrawals, and screen failures, we conservatively estimate that 44 people will need to be consented and screened in order to arrive at this target number of 24.

XII. Future Research

XII.1

Do you wish to keep any information about subjects involved with this research project so that members of the current research team may contact them in the future for your own research projects?

Yes

XII.2

Do you wish to keep any information about subjects involved with this research project so that [other researchers](#) may contact them for future research?

No

XII.3

List the data or information you will keep:

Name

Race/ethnicity

Birthdate

Sex

Contact information (mailing address, e-mail address, phone number)

XII.4

Does this project involve storing any data, tissues or specimens for future research?

Yes – contribution for future use is optional

XII.5

Describe how you will keep track of those who consent to future use and those who do not and how you will prevent future use for those who do not consent.

We will keep track of who consents to future use on our enrollment log.

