In this study, we use the blood vessels in the skin as a representative vascular bed for examining mechanisms of microvascular dysfunction in humans. Using a minimally invasive technique (intradermal microdialysis for the local delivery of pharmaceutical agents) we examine the blood vessels in a dime-sized area of the skin in healthy young women and men. As a compliment to these measurements, we also draw blood from the subjects and measure circulating factors that may contribute to cardiovascular health.

I.5 *Specify your research question(s), study aims or hypotheses (do not indicate "see protocol")*
The aim of this proposal is to define the mechanistic role of activation of AT2Rs in young men and young women. To accomplish this aim, we will test the following hypotheses:

Hypothesis 1: AT2R activation (C21) will have greater microvascular dilation in young women vs young men.
Hypothesis 2: The dilatory response to C21 will be enhanced in both young women and men with AT1R inhibition (losartan) vs control.

I.6 *Background and significance and/or Preliminary studies related to this project.
(do not indicate "see protocol")*

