Pre-menopausal women have a significantly lower incidence of cardiovascular disease (CVD) than age-matched men due to the protective benefits of estrogen. Estrogen decreases levels of Angiotensin II, allowing less Angiotensin II to act on its receptors: AT1Rs (cause constriction) and AT2Rs (cause dilation). Excess Angiotensin II disrupts the balance between these two receptors in the body acts mainly through AT1Rs, leading to higher risk of CVD and related diseases. Because estrogen downregulates Angiotensin II, there is a balance between activation of AT1Rs and AT2Rs. In young males, this balance can be dysregulated when excess Angiotensin II is produced. A new pharmacological agent, known as Compound 21 (C21), activates AT2Rs to cause vasodilation. Besides vasodilation, activation of AT2Rs with C21 also elicits anti-inflammatory and anti-fibrotic effects in animal models. In humans, this compound has been shown to cause dilation in the lungs and the peripheral vessels (e.g., skin) when given orally. Thus, the purpose of this study is to determine the extent that dilation with AT2R activation differs in young men and women. As young women have more protection from heart diseases than age-matched young males, we propose that activation of AT2Rs will be more sensitive in young women than in young men. This will help us better understand why women have enhanced cardio-protection prior to menopause.

I.7 *Literature cited / references (if attaching a grant or protocol enter N/A).*
N/A

II. Research Team

II.1 *Principal Investigator*

Name	E-mail	College
[name]	[contact]	College Lib Arts and Sciences

II.2 *Team Members*
UI Team Members

Name	E-mail	College	Contact	Key Prsn	UI COI	VAMC COI	Consent Process Involvement	Deactivated
[REDACTED]		College Lib Arts and Sciences	Yes	Yes	No		Yes	No
[REDACTED]		College Lib Arts and Sciences	No	No	No		Yes	No
[REDACTED]		Carver College of Medicine	No	Yes	No		No	No
[REDACTED]		Graduate College	No	No	No		Yes	No
[REDACTED]		College of Liberal Arts and Sciences	No	No	No		No	No
[REDACTED]		Carver College of Medicine	No	No	No		No	No
[REDACTED]		Graduate College	No	No	No		Yes	No
[REDACTED]		College of Liberal Arts and Sciences	No	No	No		No	No

Non-UI Team Members

Name Institution Location FWA Role DHHS Contact Key Prsn UI COI VAMC COI Consent Process Involvement Email

Nothing found to display.

II.3 *The Principal Investigator of this study is:*
Faculty

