Subjects will be excluded for any of the following reasons: 1) known skin allergies, skin disorders, or skin diseases such as Raynaud's phenomenon or other history of cold intolerance, 2) diagnosed or suggested history of metabolic or cardiovascular disease, 3) taking medications that could alter vascular function, including antidepressants, anxiety medications, or cholesterol or blood pressure lowering drugs, 4) oligo- or amenorrhea, 5) women that are pregnant or nursing, 6) currently tobacco use, 7) a body mass index <18 kg/m² or >30 kg/m², 8) allergy to materials used during the experiment (e.g. latex).

Because sex hormones may influence skin blood flow mechanisms, all young women will be eumenorrheic, and will be tested during the low hormone phase of the menstrual cycle (within 7 days of cessation of menses), or taking oral contraceptives.

VI.14 *Provide an estimate of the total number of subjects that would be eligible for inclusion in each of your study populations (include your control population if applicable)*

We will recruit subjects from Johnson and surrounding counties in Iowa. The University of Iowa has a student population of ~25,000 undergraduates, a majority of whom would qualify for the study based on age.

VI.15 *Describe how you will have access to each of your study populations in sufficient number to meet your recruitment goals.*

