If subjects' responses to the online screening survey deem them eligible, they will be contacted by a member of the research team via phone to confirm their answers to the pre-consent online survey, answer additional questions, and schedule a study visit.

VII.D.21 *Will you keep a screening log or other record that would include information on people who do not enroll in the study?*
Yes

VII.D.22 *Describe the information being collected and the purpose for keeping this information.*

The following information will be collected in a screening log:

1. Subject's name
2. Age
3. Sex
4. How they heard about study
5. Date that they contacted the study
6. How they contacted us (phone/email)
7. Date of phone screening
8. Phone number
9. Email address
10. Pass online screening: yes or no
11. If did not pass online screening, reason?
12. Pass phone screen? Yes or No
13. If did not pass phone screen, reason?
14. If passed phone screening, date of consent
15. Signed informed consent

VII.D.23 *Will this information be shared with anyone outside the UI research team members?*
No

VII.D.25 *After the subject agrees to participate (signs consent), are there any screening procedures, tests, or studies that need to be done to determine if the subject is eligible to continue participating?*
Yes

VII.D.26 *List and describe screening*

Complete the participant info survey (see attached RedCap document "participant info survey") for study records

Medical history and physical exam

Resting blood pressure and heart rate

Height and weight measurements

Women must complete a urine pregnancy test

VII.D.27 *Discuss how much time a potential subject will have to agree to consider participation and whether or not they will be able to discuss the study with family/friends before deciding on participation.*
There is no time limit for the subject to agree to consider to be in the study as long as the study is actively recruiting subjects and they are still eligible. Subjects are allowed to discuss the study with family/friends before deciding on participation.

VII.D.28 *How long after the subject agrees to participate do study procedures begin?*

The procedures in visit 1 (screening visit) can occur on the same day as consent. The experimental visits will begin within 2 weeks or less of visit 1.

VII.D.29 *Provide a description of the enrollment and consent process for adult subjects*

- *Describe each study population separately including control population*

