Visit 2- Experimental Visit (approximately 4 hours)

Note: In the event of an experimental failure (e.g. equipment stops working, building power outage during study visit, etc) subjects may be asked to repeat a trial.

Experimental procedures

Regularly menstruating women and women taking hormonal contraceptives will be tested during the early follicular/placebo phase to minimize variability due to circulating sex-steroid hormones. Participants will be asked to fast 3 hours prior, avoid alcohol and forms of heavy exercise 24 hours prior, avoid caffeine 12 hours prior, and avoid supplements and over-the-counter medications the morning of the experimental visit. Participants should NOT stop taking medications as prescribed by their physician.

Subjects will come to the Pharmaceutical Sciences Research Building (PSRB) and be escorted by a member of the research team to 118 PSRB for the blood draw and experiment (intradermal microdialysis). A blood draw involves a research nurse or trained lab personnel drawing blood (15 ml, ~1 Tablespoon) for substances of interest (e.g. reactive oxygen species) and blood chemistry.

Microdialysis Probe Insertion: (NOTE: The intradermal microdialysis insertion procedure used here is identical to the one approved in IRB #201909818, #202006148, #202009357, #202203433, and #202104188) Please see the attached "intradermal microdialysis" document for general information about intradermal microdialysis, schematic representation of the procedure, and references. The researchers place a tight band around the forearm so they can visualize veins. For each MD site, they make pairs of pen-marks on the arm 2.5 cm (1 inch) apart and away from veins. They remove the tight band. The MD tubing enters and exits the skin at the marks. The researchers clean the arm with povidone iodine and alcohol, and place an ice bag on the site for 5 minutes to numb the skin. Then they insert a thin needle into the skin at each entry mark. The needle's tip travels between the layers of skin for 2.5 cm (1 inch) and exits the skin at the matching exit-mark. They thread the microdialysis tubing through the

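### Do the differently worded rules in VI.13 and VII.E.6 on when women are tested leave hormone exposure uncontrolled in the comparison of women with men?

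*Combined protocol and SAP*

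**What the plan says.** Three sections of the application bear on the timing.

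- **VI.13 (subject populations and eligibility).** It states that "all young women will be eumenorrheic" and that they "will be tested during the low hormone phase of the menstrual cycle (within 7 days of cessation of menses), or taking oral contraceptives". The exclusion list includes "oligo- or amenorrhea".
- **VII.E.6 (Visit 2 procedures).** It states that regularly menstruating women and "women taking hormonal contraceptives will be tested during the early follicular/placebo phase to minimize variability due to circulating sex-steroid hormones".
- **VII.D.28 (time from consent to procedures).** It states: "The experimental visits will begin within 2 weeks or less of visit 1".

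The comparison affected is the first hypothesis in I.5, that "AT2R activation (C21) will have greater microvascular dilation in young women vs young men". Section I.6 supplies the reasoning: "Estrogen decreases levels of Angiotensin II, allowing less Angiotensin II to act on its receptors". Section XI.2 plans for 12 women and 12 men to complete the study.

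**The concern.** VI.13 and VII.E.6 both give control of sex hormones as their reason, yet they differ in three ways. VI.13 mentions pill use without a pill phase, while VII.E.6 requires the placebo phase. VI.13 names oral contraceptives, while VII.E.6 covers hormonal contraceptives generally and neither says what to do about products without a placebo phase. For naturally cycling women, VI.13 counts days from the end of bleeding, while VII.E.6 names the early follicular phase and gives no days. Neither section refers to the other or says which governs.

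If staff worked from VI.13 alone, women on active pills could be pooled with women tested at low hormone levels. The women's group in the first hypothesis would then mix different hormone exposures, and estrogen is the proposed mechanism. With 12 women, each contributes 1/12 = 8.3% of the group mean. The losartan comparison in the second hypothesis is made within each participant and is less exposed. The two-week limit appears to push in the wrong direction, because VI.13 alone makes it easier to meet.

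**Working it through.** The plan states no figure on this point, so the main check is to set the rules side by side.

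**1. Can one test day satisfy both sections?**

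| Group | VI.13 | VII.E.6 | A day that meets both |
|---|---|---|---|
| Pill users | no phase given | placebo phase | any placebo day |
| Other hormonal users | not named, and not listed as excluded | placebo phase | a placebo day, where the product has one |
| Cycling women | up to seven days after bleeding stops | early follicular, no days given | any day in the VI.13 window that counts as early follicular |

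For pill users the answer is yes: VII.E.6 is the narrower statement and lies inside VI.13. For other hormonal users, the requirement for regular cycles and the exclusion of absent or infrequent periods may remove some women whose product has no placebo phase. For cycling women, if bleeding is assumed to last 3 to 7 days, the VI.13 window runs from cycle days 4–10 to cycle days 8–14. VII.E.6 gives no days to set against this, so a conflict cannot be shown.

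**2. How often do the rules diverge for pill users?** Assume a 28-day pack with 4 to 7 consecutive placebo days; the documents give neither number. Days allowed by VI.13 but not by VII.E.6:

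- 7 placebo days: (28 − 7)/28 = 21/28 = 75%
- 4 placebo days: (28 − 4)/28 = 24/28 = 86%

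This is simply the active-pill share of the assumed pack. It does not forecast when women will be tested.

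**3. Does the two-week limit force a breach?** With L placebo days, the number of Visit 1 pack days that have a placebo day within the next 14 days is 14 + L − 1.

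- L = 4: 17 of 28, leaving 11 of 28 (39%) without one
- L = 7: 20 of 28, leaving 8 of 28 (29%) without one

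If the day of Visit 1 also counts, 10 of 28 (36%) and 7 of 28 (25%) are without one. This clash is between VII.E.6 and VII.D.28, and it would exist whatever VI.13 said. Booking Visit 1 on one of the other 17 to 20 days avoids it.

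**4. What would be at stake in H1?** Let p be the share of the 12 women tested on active pills and s the amount by which their response is lower. With the planned difference of 10 points from XI.2, the expected difference is 10 − p × s.

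- Invented values p = 0.25, s = 5: 10 − 1.25 = 8.75
- Invented values p = 0.25, s = −5: 10 + 1.25 = 11.25
- VII.E.6 followed: p = 0, so the difference stays at 10 whatever s is

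The documents supply neither p nor s, not even the sign of s.

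**The case for a change.** The strongest reply is that VI.13 is not purely an eligibility statement: it says when women will be tested, and no sentence gives VII.E.6 priority. A coordinator could book a pill user from the eligibility section alone, and the two-week limit would make that convenient. Nor is there a clear safety net in the analysis. XI.1 mentions confounders as covariates only in general terms, and the blood draw in VII.E.6 names no sex-hormone assay.

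Part of this stands. The wording is uneven, the contraceptive scope differs, and the window for cycling women is not defined in the same terms in both places. But the harm requires the team to run the experimental visit without following the instructions written for it, and nothing in the documents suggests that. The sentence in VI.13 also has another natural reading, in which pill use is an alternative to having regular natural cycles, as a condition for entry. On that reading VI.13 is silent on pill phase and VII.E.6 fills the silence.

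Recording cycle day, contraceptive type and pill day would be harmless. No planned analysis uses them by name, however, and the attached questionnaires, which were not supplied, may already collect them.

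**Conclusion.** The concern does not call for a change. The eligibility section is looser than the Visit 2 procedure, and the procedure narrows it. Followed as written, the application tests no pill user on active pills, so p = 0 and this route does not shift the comparison of women with men. The 75% to 86% and 25% to 39% figures rest on an assumed pack. The first describes the pack and the second a scheduling constraint that timing Visit 1 resolves; neither measures bias in H1.

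This rests on two assumptions: that staff use the Visit 2 instructions when running Visit 2, and that the separate written protocol listed at VII.B.11, which was not available, says nothing to the contrary. What remains is an editorial mismatch between VI.13 and VII.E.6, which the investigator may tidy when the form is next revised. The sample size, the comparison and the planned analysis are unaffected.
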